9.3 Safety Interim Analyses

The safety analyses will monitor TOX as defined above using the methods of Thall et al[9]. If there is high probability that the underlying TOX rate is greater than 15%, the trial will be held

until all treated patients have completed 30 days post-surgery or gone off study prior to that time. The trial will then be stopped early if the risk of severe toxicity has been confirmed. Formally, denoting TOX probability by p_{TOX} and assuming this follows a beta (1, 1) prior distribution, the trial will be held if $\text{Prob}(p_{TOX} > 0.15 \mid \text{data}) > 0.95$. Monitoring will start once the 5th patient has been on trial for 4 weeks (at the end of the first week of cycle 2). After that, monitoring will continue monthly until the 20th patient has been followed for the full treatment period. A 6th patient will only be enrolled once there is sufficient evidence that fewer than 2 patients have TOX, i.e. ≥ 4 of the first 5 patients complete 30 days after surgery with no TOX. For the purposes of ongoing monthly trial monitoring, patients will be evaluable if they have been treated and then either have a TOX or have gone 4 weeks without TOX. Patients who are without TOX at 4 weeks, but who develop TOX later within the treatment interval will count as having a TOX at the next monthly evaluation. Stopping rules and operating characteristics were calculated in MultcLean 2.1.

Note, that since we expect enrollment of 1-2 patients per month, it is possible that monthly monitoring may allow a small overrun of patients, but this is expected to be only 1-2 additional patients at any given look.

If there are this many (or more) patients with TOX:	2	3	4	5	6
Stop the trial if there are this many (or fewer) patients who are evaluable for TOX:	5	9	13	17	20*

*Always stop with 20 patients, but if 6 or more patients have a TOX event, then pembrolizumab is unsafe for 'window of opportunity' use at this dose and schedule.

The operating characteristics of this design based on simulations are summarized in the following table. Note, since accrual will continue during monitoring, it's possible that these results underestimate the numbers of patients by 1-2 patients at the higher TOX rates.

True Prob(TOX)	Pr(stop)	Median # Pts (25%, 75%)
0.05	0.03	20 (20, 20)
0.10	0.11	20 (20, 20)
0.15	0.25	20 (16, 20)
0.20	0.43	20 (5, 20)
0.25	0.60	12 (5, 20)

0.30	0.75	7 (5, 19)
0.35	0.86	5 (5, 12)
0.40	0.93	5 (5, 8)

The Investigator is responsible for completing a safety summary report and submitting it to the IND office Medical Monitor for review. This should be submitted after the first 5 evaluable patients complete 4 weeks of study treatment prior to cystectomy, and monthly thereafter. On every new report submission, the information from previous reported patients will need to be updated, and the information from new patients added

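### The first stopping boundary in Section 9.3 (2 TOX among 5 or fewer) has no look before the 5th patient reaches 4 weeks, and the wait cannot change the decision

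*Combined protocol and SAP*

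**What the plan says.** All of the following is in Section 9.3 unless noted.

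- **Boundary table.** The top row reads "If there are this many (or more) patients with TOX" and the row below reads "Stop the trial if there are this many (or fewer) patients who are evaluable for TOX". The pairs are 2/5, 3/9, 4/13, 5/17 and 6/20, so the first column covers 2 TOX among 5 evaluable patients or fewer.
- **Underlying rule.** "If there is high probability that the underlying TOX rate is greater than 15%, the trial will be held", with a posterior cutoff of 0.95, "assuming this follows a beta (1, 1) prior distribution".
- **Evaluability.** "patients will be evaluable if they have been treated and then either have a TOX or have gone 4 weeks without TOX". A treated patient with TOX therefore counts at once.
- **First look.** "Monitoring will start once the 5th patient has been on trial for 4 weeks". The first safety report to the medical monitor is also tied to five patients reaching 4 weeks.
- **Gate.** "A 6th patient will only be enrolled once there is sufficient evidence that fewer than 2 patients have TOX".
- **Accrual.** "we expect enrollment of 1-2 patients per month".

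Section 9.1.1 defines TOX over roughly three months: 6 weeks of treatment, 2 weeks of scheduling and 30 days after surgery. Section 5.3 has separate rules. Enrolment stops after one drug-related toxicity that makes cystectomy impossible. The 17 patients after the first 3 follow only if fewer than two of those 3 have a drug-related event above grade 3.

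**The concern.** The table's first column is met by 2 of 2, 2 of 3 and 2 of 4, but no look is scheduled at which those results could act. The gate protects patient 6 onwards; nothing in 9.3 itself holds patients 3, 4 or 5. If two of the earliest patients have TOX, later patients in the first five could be treated after the plan's own boundary has been crossed. A minimum number of patients before the first look normally guards against stopping on too little evidence. Here it cannot do that for the 2-TOX boundary, because the same two events still force a stop at five.

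**Working it through.** **1. The boundary is met before five patients.** With a beta(1,1) prior and x TOX in n patients, the posterior probability that the rate exceeds 0.15 equals P(Bin(n+1, 0.15) ≤ x).

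| TOX / evaluable | Posterior | Above 0.95? |
|---|---|---|
| 2/2 | 1 − 0.15³ = 0.9966 | yes |
| 2/3 | 0.9880 | yes |
| 2/4 | 0.9734 | yes |
| 2/5 | 0.9527 | yes |
| 2/6 | 0.9262 | no |

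The formula and the table agree that 2 TOX is a stop at every n from 2 to 5.

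**2. Reproduce the plan's figures.** I used an exact binomial recursion over the table, one patient at a time, with looks from n = 5. The probability of stopping before patient 20 is 0.0268, 0.1128, 0.2546, 0.4293, 0.6045, 0.7532, 0.8620 and 0.9314 at rates 0.05 to 0.40. The plan states 0.03, 0.11, 0.25, 0.43, 0.60, 0.75, 0.86 and 0.93, so the column is reproduced to within 0.005. Medians and quartiles also match, except for a lower quartile of 17 against a stated 16 at 15%. Section 9.2 quotes different stopping probabilities (68%, 16%, 0.7%); that is a separate matter and does not bear on this point.

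**3. Start the looks at n = 2.** Any sequence with at least 2 TOX among the first 2, 3 or 4 patients has at least 2 among 5. The set of stopping sequences is therefore the same, and the recursion returns the same Pr(stop) at every rate. Only the time of stopping moves.

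**4. Upper bound on patients spared.** If outcomes are known at once, patient k+1 (k = 2, 3, 4) is spared when the first k include at least 2 TOX. The mean spared is the sum of those three probabilities.

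| True rate | k=2 | k=3 | k=4 | Mean spared | Expected N, looks from 5 → from 2 |
|---|---|---|---|---|---|
| 15% | 0.0225 | 0.0607 | 0.1095 | 0.19 | 16.72 → 16.52 |
| 30% | 0.0900 | 0.2160 | 0.3483 | 0.65 | 10.44 → 9.78 |
| 40% | 0.1600 | 0.3520 | 0.5248 | 1.04 | 7.54 → 6.50 |

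The gate before patient 6 makes 3 the maximum in any one trial.

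**5. Allow for lag.** Assumptions, not in the plan: evenly spaced entry; a TOX window of 6 + 2 + 30/7 = 12.3 weeks; each event known when it occurs; Section 5.3 rules ignored.

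*TOX only at weeks 8 to 12.3, one patient per month (4.35 weeks apart).* Both events in patients 1 and 2 are known before patient 5 enters. The second is known before patient 4 enters only if it falls in the first 0.7 of the 4.3 weeks, a fraction of about 0.16. The same fraction applies to an event in patient 3 being known before patient 5 enters. At a 30% rate the mean spared is 0.09 × 1.16 + (2 × 0.3 × 0.7 × 0.3) × 0.16 = 0.104 + 0.020, or 0.12 to 0.13 depending on how a month is converted to weeks. The corresponding values at 15% and 40% are about 0.03 and 0.22.

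*Same timing, two per month.* Patient 5 enters at about week 8.7, before any TOX in patient 2 can be known (week 2.2 + 8 = 10.2). The mean spared is 0.

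*TOX spread evenly over weeks 0 to 12.3, 30% rate.* Evaluated numerically, the mean spared is 0.35 at one per month and 0.12 at two per month.

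**6. What must not be changed.** The posterior formula at 1 of 1 gives 1 − 0.15² = 0.978, above the cutoff. Applying it from the first patient would raise Pr(stop) at a 15% rate from 0.258 to 0.321 (both counting a crossing at n = 20).

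**The case against.** The strongest reply is that Section 5.3 already acts early on much of TOX, and sometimes more strictly. One drug-related toxicity that rules out cystectomy ends enrolment. On a plain reading, so does a drug-related death before surgery. Death is grade 5, so two drug-related deaths among the first 3 patients also fail the first-cohort gate. If that gate is observed, patients 4 and 5 wait for the first 3, although the length of the wait is not given. This stands and narrows the point. A reader might infer that nothing protects patients 3 to 5, or that early toxic deaths would pass without action. The documents do not support that.

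What 5.3 leaves open is mainly three kinds of case:

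- grade 3 surgical complications within 30 days that are possibly related to treatment, which fall below the above-grade-3 gate and, if there are two, below the general three-patient count;
- deaths attributed to surgery rather than to the drug;
- pairs of events not both within the first 3 patients, for example patients 1 and 4.

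A second reply is that table and text do not contradict each other. The first look is triggered by five patients on trial, while the table counts evaluable patients. If one of five leaves before 4 weeks without TOX, the look has four evaluable and the words for fewer than five do act. This also stands: the schedule can be carried out as written, and a minimum number before the first look is an ordinary choice. It does not show any benefit from the wait at this boundary.

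A third reply is that surgical events come late relative to accrual, so little exposure is saved. The lag figures bear this out.

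**Conclusion.** The point holds as a cheap improvement, not as an error. Under 9.3, two TOX among the first 2 to 4 patients do not hold entry of the remaining patients up to the 5th, and delaying the hold cannot alter whether the trial stops. The invariance is exact for the 2-TOX boundary, treating each counted outcome as final. It does not extend to the raw posterior rule at 1 of 1.

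The benefit is small: at most three patients in one trial. The mean spared is no more than 0.19, 0.65 and 1.04 at rates of 15%, 30% and 40% with immediate outcomes, and well below that once lag is allowed for. The lag figures rest on assumed even accrual and event timing, and they ignore Section 5.3, which would reduce them further. A reader might infer from this that the published stopping probabilities in 9.3 are wrong. They are not: they reproduce, and they stay the same after the change.

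**What to change.** Add to Section 9.3 that the first column of the existing table applies from the first patient: accrual is held once two patients have TOX, even if fewer than five are evaluable. State that the posterior formula is not applied to 1 of 1. In the same edit, reconcile the 3-patient gate in Section 5.3 with the 5-patient gate in Section 9.3, so that it is clear which governs entry of patients 4 and 5.

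The cost is a short amendment and a re-run of the patient-count column. Sample size, false-stop probability and the Pr(stop) column are unchanged. With immediate outcomes, the lower quartile of patients moves from 5 to 4 at rates of 25% and 30% and from 5 to 3 at 35% and 40%. The median at 40% moves from 5 to 4.

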2.1.7 Criteria for Evaluation

Safety Measure: Safety will be evaluated for all treated patients using the National Cancer Institute (NCI) Common Terminology Criteria for Adverse Events v4.0 (CTCAE). Safety assessments will be based on medical review of adverse event reports and the results of vital sign measurements, physical examinations, and clinical laboratory tests. The incidence of adverse events will be tabulated and reviewed for potential significance and clinical importance.

Efficacy Measure: Treatment efficacy of patients treated with pembrolizumab will be through histopathologic examination of the final radical cystectomy specimen. Those patients with NMIBC who achieve a complete response (pT0) and those with MIBC who are found to harbor only residual NMIBC (\leq pT1) will be considered responders.

Biological Activity: Tissue immune response and activation will be evaluated as described earlier. This will include a comparison of post-treatment tissue to pre-treatment tissue from the same patient when available and to similar patients when not.

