5.3 Randomization or Treatment Allocation

Patients will be enrolled sequentially without randomization. According to a standardized, dose escalating, phase 2 safety design a total of 20 patients may be enrolled.

Initially 3 patients will be studied at 200 mg given at weeks 1 and 4 by IV infusion. These patients will be followed for safety assessments every 3 weeks during the treatment phase and at 30 and 90 days post-op visits during the follow-up phase. If < 2 patients in the initial cohort of 3 experience a grade >3 drug related adverse event then a subsequent cohort of 17 patients at 200 mg dose will be enrolled.

The following stopping rules will apply: if at any time ≥ 3 patients experience a drug related grade 4 adverse event including bowel perforation or any drug related grade 3 skin or gastrointestinal adverse event without clinical improvement within 2 weeks of study drug discontinuation and/or initiation of corticosteroid therapy to treat the adverse event; no additional patients will be enrolled. If any grade 3 or higher adverse event that is possibly, probably or definitely related to study drug, with the exception of any grade 3 or higher adverse events that is potentially treatable with steroids and improves to grade 1 or better within 2 weeks of steroid therapy initiation and/or study treatment discontinuation, the above stopping rule would apply. Also excluded will be grade 3 lipase elevation as this is common with this agent but is almost universally asymptomatic. Grade 4 lipase elevation will be criteria for stopping. If during monitoring, a patient is found to have disease progression within the treatment study period then this will be counted as a grade 4 toxicity event and the above stopping rule would apply. If there is a >12 week delay to surgery due disease progression, then this will be counted as a grade 4 toxicity event and the above stopping rule would apply. If a patient suffers a drug related toxicity which results in an inability to perform

radical cystectomy further study enrollment will be stopped. If there is a > 12 week delay to surgery due to a drug related toxicity in 2 or more patients, further enrollment will be stopped. Once patients have received a maximum of two doses of pembrolizumab, they will undergo surgery at approximately 6 - 8 weeks. An assessment of tumor response will not be made prior to radical cystectomy.

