9.2 Endpoints

9.1.1 Toxicity for Safety Monitoring (TOX)

TOX will be monitored for an approximate 3-month treatment time interval (2 cycles/6 weeks + surgery/2 week scheduling cushion + 30 day surgical complication evaluation). A patient will be considered to have a toxicity of concern (TOX) if any of the following apply:

- Any 30-day grade 3 or higher surgical complication at least possibly related to the treatment
- Any toxicity at least possibly related to the treatment that prevents surgery
 - Note, missing surgery due to progression or withdrawal will not count as a TOX event. Rapid progression is not seen with pembrolizumab.
- Death between the start of study and the 30-day post-surgical assessment will count as long as it is toxic death at least possibly related to the pembrolizumab or surgery. Deaths clearly unrelated to treatment will not count as an event.

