9.4 Analysis Plan

TOX events will be reported with a 95% credible interval assuming a non-informative prior of beta (1,1). Specific events will also be summarized. Then all adverse events and surgical complications will be reported overall by grade, attribution, and treatment period (cycle 1, cycle 2, between the end of cycle 2 and actual surgery, 30 days following surgery). Demographic and baseline laboratory results will be summarized using descriptive and graphical statistics. Changes in markers between biopsy and surgical resection will be compared with a paired t-test or non-parametric alternative as indicated for continuous measures, and with McNemar's test for binary or ordinal measures. The numbers of patients with sufficient samples for laboratory analysis will be used to plan the numbers of patients needed for enough evaluable samples future trials. Similarly this experience will guide planning for the numbers and types of markers that can be reasonably assessed from surgical specimens in this patient population after 'window of opportunity' pembrolizumab treatment.

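### As worded in section 9.3, the gate for patient 6 can never be met if two of the first 5 patients miss surgery for a reason that 9.1.1 says is not TOX

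*Combined protocol and SAP*

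**What the plan says.** Section 9.3 (Safety Interim Analyses) states the aim of the gate: "A 6th patient will only be enrolled once there is sufficient evidence that fewer than 2 patients have TOX". An i.e. clause then gives the working rule, that at least "4 of the first 5 patients complete 30 days after surgery with no TOX".

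Section 9.1.1 defines TOX. Surgery prevented by toxicity at least possibly related to treatment is TOX. Other missed surgery is not: "Note, missing surgery due to progression or withdrawal will not count as a TOX event".

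Three further provisions bear on the point.

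- The hold rule in 9.3 provides for early leavers. The trial is held "until all treated patients have completed 30 days post-surgery or gone off study prior to that time". The gate has no such clause and no replacement rule.
- For monthly monitoring, 9.3 counts a treated patient as evaluable after TOX or after 4 weeks free of it. Surgery is not required.
- Section 5.3 says that a patient who "is found to have disease progression within the treatment study period then this will be counted as a grade 4 toxicity event". Such events count toward a limit of 3 or more patients. Withdrawal has no count there.

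**The concern.** The aim and the working rule agree only if every patient without TOX has surgery. Section 9.1.1 allows for patients who do not. A patient who never has a cystectomy cannot reach day 30 after it, so two of them among the first 5 leave at most 3 possible completers. The rule names the first 5, so no later patient can make up the number.

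Enrolment in a 20-patient study could then end at 5 patients for a reason that the plan itself says is not toxicity. The alternative is that the team chooses between two readings of a safety gate during the trial, with the outcomes already known.

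**Working it through.** **Inputs from 9.3.** Beta(1,1) prior; TOX limit 15%; posterior cutoff 0.95; printed boundaries of 2, 3, 4, 5 and 6 TOX at up to 5, 9, 13, 17 and 20 evaluable patients; gate of at least 4 of 5. **Assumed:** m, the chance that a patient misses surgery without TOX. The documents give no value, so 1% to 20% is shown.

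**1. Reproduce the plan's figures.** The smallest x with P(p > 0.15 | Beta(1+x, 1+n−x)) > 0.95 returns all five printed boundaries. Exact binomial recursion, with a look after each patient from n = 5 to 19, gives:

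| True TOX | 0.05 | 0.10 | 0.15 | 0.20 | 0.25 | 0.30 | 0.35 | 0.40 |
|---|---|---|---|---|---|---|---|---|
| Recomputed | 0.027 | 0.113 | 0.255 | 0.429 | 0.605 | 0.753 | 0.862 | 0.931 |
| 9.3 table | 0.03 | 0.11 | 0.25 | 0.43 | 0.60 | 0.75 | 0.86 | 0.93 |

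Adding a look at n = 20 gives 0.027 at TOX 5% and 0.258 at TOX 15%. The TOX boundaries alone therefore account for the table, which is indexed by true TOX probability only. If all 5 patients have surgery, the gate (fewer than 2 TOX in 5) is the same event as not crossing the boundary of 2 in 5, so it adds nothing to these figures. Missed surgery separates the two. (Section 9.2 prints other stopping probabilities. That is a separate matter and does not affect this point.)

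**2. The case that blocks.** Two of the first 5 miss surgery for progression or withdrawal, with 0 TOX.

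- Completers: at most 5 − 2 = 3, below the 4 required.
- Stopping table: 0 TOX against a boundary of 2, not crossed.
- Section 5.3: at most 2 progression events against a limit of 3, so it need not stop enrolment.

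**3. Size with zero TOX.** P(block) = 1 − (1−m)^5 − 5m(1−m)^4. At m = 5%: 1 − 0.7738 − 0.2036 = 0.0226.

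| m | 1% | 3% | 5% | 10% | 20% |
|---|---|---|---|---|---|
| P(block) | 0.1% | 0.8% | 2.3% | 8.1% | 26% |

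**4. Size with TOX 5%.** Treat TOX and non-TOX missed surgery as mutually exclusive, so that a patient fails the gate with probability f = 0.05 + m. P(gate not met) is the formula in step 3 with f in place of m. Fewer than 2 TOX in 5 fails with probability 0.023 whatever m is.

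| m | 3% | 5% | 10% | 20% |
|---|---|---|---|---|
| Gate as worded not met | 0.054 | 0.082 | 0.165 | 0.367 |
| Of which fewer than 2 TOX | 0.032 | 0.059 | 0.142 | 0.345 |

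The second row is the first minus 0.0226, taken before rounding. It covers two or more misses, and one miss together with one TOX.

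**5. Whole trial at TOX 15%.** With the gate as worded followed by the printed boundaries, the chance of ending early rises from 0.258 to 0.339 at m = 5% and 0.429 at m = 10%.

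**The case against.** The strongest reply is that the aim asks for sufficient evidence, not merely for fewer than 2 observed events. TOX includes surgical complications within 30 days, and a patient without surgery supplies no evidence on those. Asking for four post-surgical completers can therefore be a deliberate safeguard. This stands, and it is why the fix keeps the number 4. It does not explain why the gate has no way forward when patients leave early, while the hold rule in the same section has one.

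The second reply is that missed surgery should be uncommon. Patients are already scheduled for cystectomy (2.2), must be good surgical candidates without metastases (5.1.2), and 9.1.1 says that rapid progression is not seen with this drug. This also stands: at 1% to 3% the block with zero TOX is below 1%. The larger figures need 10% to 20% missed surgery, which nothing in the documents supports or excludes.

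A reader might go further and infer that the safety report itself is faulty. Section 2.1.7 says "Safety will be evaluated for all treated patients", so patients without surgery stay in the denominator, and 9.4 plans no count of missed or delayed cystectomies. The documents do not support calling that an error. Surgery prevented by treatment-related toxicity is already TOX, and 9.4 summarises specific events. The number operated on follows from the specimen endpoints in 2.1.7 and 9.1.4. Moving the denominator from 20 treated to 16 operated changes 3 TOX from 15% (5.4% to 36.3%) to 18.8% (6.8% to 43.4%), with 3 events against a final limit of 6 either way. No decision changes.

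**Conclusion.** The point holds as a drafting conflict in the 9.3 gate. Two non-TOX misses among the first 5 make the working rule impossible to meet even with zero TOX, and the printed operating characteristics do not allow for this. That much follows from the wording and needs no assumed rate.

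The size does depend on a rate. With zero TOX it is 0.1% at 1% missed surgery, 2.3% at 5% and 26% at 20%, assuming that patients miss surgery independently of one another.

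Two stronger readings should not be drawn. One is that the 9.1.1 exclusion is wrong: it is stated openly and is an acceptable choice. The other is that the trial is likely to end at 5 patients: at low missed-surgery rates it is not, and a team following the stated aim might enrol patient 6 anyway. The plan should settle the matter beforehand because this is a safety gate, and the change is small.

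**What to change.** Replace the i.e. clause in 9.3 with wording such as:

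> Patient 6 enrols once at least 4 of the first 5 have reached day 30 after surgery without TOX. If fewer than 4 can do so because patients went off study before surgery without TOX, only the number needed to reach 4 completers will be replaced, within the total of 20. Enrolment beyond this gate cohort opens when 4 patients have reached day 30 after surgery without TOX and the 9.3 stopping boundary for the number evaluable is not crossed. The stops in 5.3 still apply.

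This keeps the post-surgical evidence and adds no boundary beyond the printed table. Replacement is needed only if two or more of the first 5 miss surgery without TOX, or if one does and another has TOX. At zero TOX that has the probabilities in step 3 of the working; at TOX 5% it has those in the second row of step 4. Each round costs about one 3-month treatment interval (9.1.1) plus accrual time.

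A simpler alternative is to copy the hold rule's off-study clause into the gate. It needs no replacements and fails only 2.3% of the time at TOX 5%, but it would admit patient 6 with fewer than 4 patients observed after surgery.

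Optionally, add a line to 9.4 giving the number of treated patients whose cystectomy was missed or delayed by more than 12 weeks, by reason. It would be useful to readers, but the fix does not depend on it.

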6.0 STUDY FLOW CHART

STUDY PHASE	SCREENING PHASE	TREATMENT PHASE				FOLLOW-UP PHASE	EARLY TREATMENT DISCONTINUATION
VISIT/CYCLE	SCREENING	CYCLE #1 (Week 1)	CYCLE #2 (Week 4)	PRE-OP/SAFETY VISIT (Week 7)	SURGERY (Week 6- 8)	FOLLOW-UP	
Scheduling window (days)	-28 to -1	1(± 3)	21(± 3)	35-49(± 3)	42-56(± 3)	30 day (± 7) and 90 day (± 7) Post Op	
Informed Consent	X						
Inclusion/Exclusion Criteria	X						
Demographics/Medical history	X						
Concomitant Medications	X	X	X	X	X	X ⁸	X ⁸
Pembrolizumab Administration		X	X				
Assessment of Disease Extent ¹	X						
Review of Adverse Events	X	X	X	X	X	X	X
Full Physical Exam	X						X
Directed Physical Exam		X	X	X		X	
Vital Signs and Weight	X	X ²	X ²	X		X	X
ECOG Performance Status	X	X	X	X		X	X
Pregnancy Test	X	X ³					
PT/INR and aPTT	X ⁹	X	X	X		X	X
CBC with Diff	X ⁹	X	X	X		X	X

Proprietary Information of MD Anderson

2017-0057

January 9, 2019

Page 28

Comprehensive Metabolic Panel ⁴	X ⁹	X	X	X		X	X
Urinalysis ⁵	X ⁹	X	X	X		X	X
T3, FT4 and TSH	X ⁹	X	X	X		X	X
Pulmonary Function Tests	X						
ACTH, Cortisol	X	X	X				
ESR, CRP	X	X	X				
Testosterone, FSH, LH (males)	X	X	X				
Estrogen, FSH, LH (females)	X	X	X				
Archival Tissue Collection ⁶	X				X		
Feces and Urine for microbiome studies	X			X		X ¹⁰	
Blood for Correlative Studies ⁷	X		X	X		X	
Cystectomy					X		

¹ A complete assessment of disease extent will be made at screening per SOC guidelines, and will include but not be limited to diagnostic endoscopy with biopsy/resection of the index lesion for pathologic diagnosis. Additionally an examination and assessment for palpable disease will be made. Cross sectional imaging of the chest, abdomen and pelvis with the addition of whole body nuclear medicine bone imaging where clinically indicated will complete the staging evaluation. Exams performed within 6 weeks prior to screening will be accepted for inclusion in the study if deemed appropriate by the treating physician

² Pre and post pembrolizumab dose during treatment administration days

³ Female subjects of childbearing potential should have a negative urine or serum pregnancy test within 72 hours prior to receiving the first dose of study medication. If the urine test is positive or cannot be confirmed as negative, a serum pregnancy test will be required.

⁴ Includes: Albumin, alkaline phosphatase, ALT, AST, LDH, electrolytes, uric acid, calcium, glucose, phosphorus, magnesium, total bilirubin, total protein, BUN and creatinine

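### After the five-patient gate, the monthly TOX boundary counts patients as non-events at 4 weeks although their TOX window stays open to 30 days after surgery, so holds come later and the stated overrun is too low

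*Combined protocol and SAP*

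**What the plan says.** Section 9.1.1 states that "TOX will be monitored for an approximate 3-month treatment time interval", made up of 6 weeks of treatment, a 2-week scheduling cushion and 30 days after surgery. A patient has TOX through any of three routes:

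- a complication of the operation: "Any 30-day grade 3 or higher surgical complication at least possibly related to the treatment"
- a possibly treatment-related toxicity because of which the operation cannot be done
- a toxic death: "Death between the start of study and the 30-day post-surgical assessment will count as long as it is toxic death"

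The flow chart (6.0) puts surgery at day 42-56.

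Section 9.3 holds the trial when the posterior probability that the TOX rate exceeds 15% is above 0.95, under a beta(1,1) prior. The boundary is 2/5, 3/9, 4/13, 5/17 and 6/20, as TOX events over evaluable patients. For the monthly looks, "patients will be evaluable if they have been treated and then either have a TOX or have gone 4 weeks without TOX". A TOX arising later is added at the next look.

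Two other steps in 9.3 wait for full follow-up. The 6th patient is enrolled only when at least four of the first five have passed 30 days after surgery without TOX. A hold is resolved only when all treated patients have reached 30 days after surgery or left the study.

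On enrolment beyond a look, 9.3 says "this is expected to be only 1-2 additional patients at any given look". The safety summary report is first due "after the first 5 evaluable patients complete 4 weeks of study treatment prior to cystectomy", then monthly.

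**The concern.** At 4 weeks a patient is about one week past the second dose and two to four weeks short of surgery. A 30-day surgical complication cannot yet have happened, and whether a toxicity will prevent surgery is usually not known. A drug toxicity that neither prevents surgery nor causes death is not TOX at all. Being TOX-free at 4 weeks therefore says little about the endpoint, yet from that day the patient carries full weight as a non-event.

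The boundary is calibrated for patients whose outcome is known. Reading it against patients whose window is open lowers the observed rate at each look and delays a hold. Safety is the primary objective, and patients 6-20 are covered by this rule. Section 9.3 gives no reason for using 4 weeks here when it uses 30 days after surgery for the gate and for confirming a hold.

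**Working it through.** **1. The plan's own figures.** With r events in n patients the posterior is Beta(1+r, 1+n-r). Its probability above 0.15 is 0.953 (2/5), 0.950 (3/9), 0.953 (4/13), 0.958 (5/17) and 0.971 (6/20), so the boundary reproduces. An exact binomial recursion, with a look after every patient from the 5th to the 19th and each outcome known at once, gives:

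| True TOX | 0.05 | 0.10 | 0.15 | 0.20 | 0.25 | 0.30 | 0.35 | 0.40 |
|---|---|---|---|---|---|---|---|---|
| 9.3 table | 0.03 | 0.11 | 0.25 | 0.43 | 0.60 | 0.75 | 0.86 | 0.93 |
| Recomputed | 0.027 | 0.113 | 0.255 | 0.429 | 0.605 | 0.753 | 0.862 | 0.931 |

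The table therefore matches a model with no outcome delay.

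**2. Length of the window.** 42 + 30 = 72 days to 56 + 30 = 86 days from first dose. The upper figure equals the 9.1.1 sum: 42 + 14 + 30 = 86.

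**3. Patients counted too early.** Expected number = monthly accrual × days / 30.4.

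| | Days | 1/month | 2/month |
|---|---|---|---|
| Counted, not yet operated (day 28 to surgery) | 14-28 | 0.5-0.9 | 0.9-1.8 |
| Counted, TOX window open (day 28 to day 72-86) | 44-58 | 1.4-1.9 | 2.9-3.8 |

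**4. Effect on one decision.** Three TOX in 8 fully followed patients gives a posterior probability of 0.966, a hold. Add two TOX-free patients with incomplete windows and 3/10 gives 0.931, no hold.

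**5. Effect on the design.** This was simulated with the five-patient gate, monthly looks and the hold-and-confirm step. Assumptions not in the documents: surgery spread over day 42-56, and all TOX falling in the 30 days after surgery. True TOX rate 0.30:

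| | 1/month, 4-week rule | 1/month, 30-day rule | 2/month, 4-week rule | 2/month, 30-day rule |
|---|---|---|---|---|
| Stop before 20 enrolled | 65% | 68% | 59% | 64% |
| Same, among trials past the gate | 34% | 39% | 22% | 30% |

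The gate alone stops 47% of trials at this rate (two or more TOX in five). With immediate outcomes the table implies (0.753 - 0.472) / (1 - 0.472) = 53% stopping after the gate. Much of the gap from 53% is outcome delay, which a new denominator does not cure. Overall Pr(stop), including stops after full enrolment, rises only 1-2 points with the 30-day rule. Another run under similar assumptions gave 56% against 62% at 2/month, so these figures are good to a few points.

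If half of TOX fell before week 4, stopping before 20 would be 70% against 71% (1/month) and 63% against 67% (2/month).

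**6. Overrun.** Overrun is taken as patients enrolled beyond the one whose outcome truly crosses the boundary. In trials that stop after the gate, it averages about 2-4 at 1/month and 4-6 at 2/month, over true TOX rates of 0.15-0.40.

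**The case against.** The best case for the plan is that its safeguards leave the 4-week rule little to spoil. The first five patients are fully followed before a sixth enters. Late TOX is added at the next look, a hold is settled on complete data, and monitoring runs until the 20th patient is fully followed. Section 5.3 also has rules that do not use this denominator: enrolment stops after one patient whose drug-related toxicity makes cystectomy impossible, after long drug-related surgical delays in two patients, and after three patients with specified drug-related events. All of this stands, and it is why the effect is modest. None of it takes incompletely followed patients out of the denominator.

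The 1-2 overrun can be defended on mean sample size. In one simulation the mean number treated was 11.6-12.2, against 10.4 with immediate outcomes, an excess of 1.2-1.8. That average includes the many trials stopped at the gate, where there is no overrun. It does not describe a trial that crosses later.

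A 30-day denominator also errs the other way, because events count at once while non-events wait. That is a real trade-off.

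Some stronger readings are tempting but not supported:

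- That counted patients have not yet been at risk. Only about 0.5-1.8 are unoperated at a look; the other open-window patients are inside their 30 days. A toxicity that prevents surgery, or a drug-related death, can arise before surgery.
- That the monthly look is what limits exposure. The gate and section 5.3 do so too.
- That the visit at "30 day (± 7) and 90 day (± 7) Post Op" can close the endpoint on day 23. Section 8.1 requires all adverse events through 30 days after surgery whatever the visit date, and they are reviewed again at day 90.

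**Conclusion.** The point holds as a flaw in the monthly rule after the gate, and it should be fixed. The rule delays holds and does not lose events. At a true TOX rate of 0.30 it costs about 3-5 percentage points of stopping before full enrolment, or 5-8 points among trials past the gate. Those figures assume that all TOX follows surgery, and the cost is smaller if some falls before week 4. The section 5.3 rules were not simulated.

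Two stated figures also need correction. The Pr(stop) table describes a trial with immediate outcomes, and an overrun of 1-2 patients is too low for trials that stop after the gate. The number of patients counted early rests only on the plan's surgery window and accrual. The stopping and overrun percentages rest on the simulation assumptions above.

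**What to change.** In 9.3, redefine evaluability for the monthly looks. A treated patient is evaluable once TOX has occurred, or on completing 30 days after surgery without TOX, or on going off study before then without TOX. TOX counts when it occurs. This is the time point 9.3 already uses for the gate and for confirming a hold.

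Re-run the operating characteristics with the actual outcome delay, accrual, gate and hold-and-confirm step, and restate Pr(stop) and the expected overrun. The stopping probabilities in 9.2 (68%, 16% and 0.7% at TOX rates of 30%, 15% and 5%) already differ from the 9.3 table (0.75, 0.25 and 0.03) and should be reconciled in the same revision. In the monthly safety report, list patients with open TOX windows separately.

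No extra patients or visits are needed. Holds that later clear rise from about 1-2% to about 2-9% of trials; one variant gave up to 14% at a true TOX rate of 0.30. Each hold is still confirmed on full follow-up. The restated figures will look less favourable. If the extra holds are unwelcome, weighting partial follow-up in a time-to-event Bayesian monitor is an alternative, at the price of a more complex rule.
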